8.1.3.1 Primary Efficacy Analysis

The primary efficacy variable will be the change from baseline to Week 52 on the PSPRS total score. The primary efficacy analysis will utilize a likelihood-based, mixed-effects model, repeated measures (MMRM) analysis of the change from baseline for each post-baseline and compare each ABBV-8E12 dose group with the placebo group. The model, which uses all observed data, will include fixed, categorical effects for treatment, site, visit, baseline score-by-visit interaction and treatment-by-visit interaction, with continuous fixed covariates for the corresponding baseline score. The primary comparison will be the contrast between each ABBV-8E12 dose group and placebo at Week 52. The treatment group differences at earlier visits will be assessed as secondary. An unstructured (co)variance structure will be used to model the within-subject errors. Satterthwaite's approximation will be used to estimate denominator degrees of freedom and the Type III sum-of-squares for the Least Square (LS) means will be used to estimate treatment group differences.

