The change from baseline score on each secondary and exploratory efficacy variable if appropriate (with the exception of CGI-C and PGI-C scores) will be summarized and analyzed using the similar MMRM model described for the primary efficacy analysis. The analyses will be performed in the ITT data set.

CGI-C scores at each post-baseline visit will be analyzed using an MMRM model, including fixed, categorical effects for treatment, site, visit, and treatment-by-visit interaction, with continuous fixed covariates for baseline CGI-S.

PGI-C scores at each post-baseline visit will be analyzed using an MMRM model, including fixed, categorical effects for treatment, site, visit, and treatment-by-visit interaction.

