Randomization and study drug administration are the last activities of the Day 1 Visit after the site completes other study procedures and verifies that the subject is eligible to participate in the study. From the definition of "baseline," it is clear that a baseline for a specific measurement is the last non-missing observation taken up to and on the Day 1 Visit (the Randomization Visit). At the computation level, the value of "baseline" for an efficacy or safety assessment is determined using the Rx Day associated with the visit. Namely, baseline value is determined by taking the last non-missing observation obtained before the time of first dosing on Rx Day 1. If an SAE occurs on the first dosing day, the event will be reported as a post baseline event and the related safety assessments will be considered post-baseline data as well.

Definition of Analysis Windows

To perform longitudinal data analysis, observations that are obtained after the first day of study drug administration will be assigned to an analysis "week" associated with the Rx Days that are corresponding to the observations. Unless otherwise specified, efficacy observations and safety observations no more than 45 days after the last dose of study drug will be included in analyses for the double-blinded period. Safety observations later than 45 days, but no more than 20 weeks, after the last dose of study drug will be included for the post-treatment follow-up period safety analysis. The intervals presented below for

each schedule visit (Rx Days X through Y) include both Rx Days X and Y. The nominal day for each scheduled visit is defined in "Activities" row in [Table 2](#).

For measurements that are planned to be collected during double-blind treatment period at Weeks 12, 24, 36, and 52, i.e., PSPRS, SEADL, PGI-C, PSP-QoL and UPDRS Part II, observations will be mapped to an analysis "week" according to the following windows defined by Rx day.

- Week 12 Rx Days 2 through 126
- Week 24 Rx Days 127 through 210
- Week 36 Rx Days 211 through 308
- Week 52 Rx Days > 308

For measurements that are planned to be collected during double-blind treatment period at Weeks 8, 20, 32, and 48, i.e., RBANS, Color Trails Test (Parts 1 & 2), letter fluency, EQ-5D, and NNIPPS-PPS, observations will be mapped to an analysis "week" according to the following windows defined by Rx day.

- Week 8 Rx Days 2 through 98
- Week 20 Rx Days 99 through 182
- Week 32 Rx Days 183 through 280
- Week 48 Rx Days > 280

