For measurements that are planned to be collected during double-blind treatment period at Weeks 8, 12, 20, 24, 32, 36, 48 and 52, i.e., CGI-S and CGI-C, observations will be mapped to an analysis "week" according to the following windows defined by Rx day.

- Week 8 Rx Days 2 through 70
- Week 12 Rx Days 71 through 112
- Week 20 Rx Days 113 through 154
- Week 24 Rx Days 155 through 196
- Week 32 Rx Days 197 through 238

- Week 36 Rx Days 239 through 294
- Week 48 Rx Days 295 through 350
- Week 52 Rx Days > 350

For measurements that are planned to be collected during double-blind treatment period at Weeks 1, 2, 4, 8, 12, 13, 14, 16, 20, 24, 28, 32, 36, 40, 44, 48 and 52, i.e., vital sign and C-SSRS observations will be mapped to an analysis "week" according to the following windows defined by Rx day. The first 30 randomized subjects represent Cohort 1 and the rest randomized subjects represent Cohort 2.

- Week 1 Rx Days 2 through 10 (Cohort 1 and Cohort J1 only)
- Week 2 Rx Days 11 through 22 (Cohort 1 and Cohort J1 subjects)
Rx Days 2 through 22 (Cohort 2 subjects)
- Week 4 Rx Days 23 through 42
- Week 8 Rx Days 43 through 70
- Week 12 Rx Days 71 through 87 (Cohort 1 and Cohort J1 subjects)
Rx Days 71 through 98 (Cohort 2 subjects)
- Week 13 Rx Days 88 through 94 (Cohort 1 and Cohort J1 only)
- Week 14 Rx Days 95 through 105 (Cohort 1 and Cohort J1 only)
- Week 16 Rx Days 106 through 126 (Cohort 1 and Cohort J1 subjects)
Rx Days 99 through 126 (Cohort 2 subjects)
- Week 20 Rx Days 127 through 154
- Week 24 Rx Days 155 through 182
- Week 28 Rx Days 183 through 210
- Week 32 Rx Days 211 through 238
- Week 36 Rx Days 239 through 266
- Week 40 Rx Days 267 through 294
- Week 44 Rx Days 295 through 322
- Week 48 Rx Days 323 through 350
- Week 52 Rx Days > 350

For measurements that are planned to be collected during double-blind treatment period at Weeks 2, 4, 8, 12, 16, 20, 24, 28, 32, 36, 40, 44, 48, and 52, i.e., body weight observations will be mapped to an analysis "week" according to the following windows defined by Rx day.

- Week 2 Rx Days 11 through 21
- Week 4 Rx Days 22 through 42
- Week 8 Rx Days 43 through 70
- Week 12 Rx Days 71 through 98
- Week 16 Rx Days 99 through 126
- Week 20 Rx Days 127 through 154
- Week 24 Rx Days 155 through 182
- Week 28 Rx Days 183 through 210
- Week 32 Rx Days 211 through 238
- Week 36 Rx Days 239 through 266
- Week 40 Rx Days 267 through 294
- Week 44 Rx Days 295 through 322
- Week 48 Rx Days 323 through 350

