10.3 Secondary Efficacy Analyses

10.3.1 Analysis of Secondary Efficacy Variables

The secondary efficacy variables include change from baseline in the following score:

- Unified Parkinson's Disease Rating Scale (UPDRS) Part II score
- Clinical Global Impression of Change (CGI-C) score (the score itself indicate change)
- Midbrain atrophy measured by volumetric MRI change from baseline
- Schwab and England Activities of Daily Living Scale (SEADL) score
- Clinical Global Impression of Severity (CGI-S) score
- PSP Quality of Life (PSP-QoL) total, subscales and VAS scores
- PSPRS domain scores
- Regional atrophy measured by volumetric MRI – third ventricle, frontal lobes, superior cerebellar peduncle, brainstem, whole brain
- PSP Staging System (PSP-SS) (composite of dysphagia and gait items from PSPRS) score
- Time to loss of ability to walk independently as measured by PSPRS item 26, which is the Rx day of the first time when the post-baseline item 26 score is 3 or 4.

UPDRS Part II score, CGI-C score, SEADL score and the midbrain atrophy measured by volumetric MRI are key secondary efficacy variables, and the Week 52 contrasts for these variables for ABBV-8E12 doses vs placebo will be included in the multiplicity adjustment for the overall FWER control. Volumetric MRI atrophy variables (third ventricle, frontal lobes, superior cerebellar peduncle, brainstem, whole brain), PSP-QoL total score and subscale and VAS scores, PSPRS domain scores, CGI-S score, PSP-SS score and time to loss of ability to walk analysis (measured by PSPRS item 26) will not be included in the multiplicity adjustment for the overall FWER control. The MMRM method used for the primary efficacy analysis will be applied to analyze the change from the baseline to each post-baseline assessment up to and including Week 52 for all secondary variables except time to loss of ability to walk independently as measured by PSPRS item 26. The model will include fixed, categorical effects for treatment, site, visit, baseline score-by-visit and treatment-by-visit interaction, with continuous fixed covariate for baseline score and the baseline score-by-visit interaction in the model. The comparison will be the contrast between each ABBV-8E12 dose group and placebo group at each post-baseline visit. For

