CGI-C analysis, the dependent variable is the CGI-C score itself, baseline CGI-S score will be used in the MMRM model as a covariate and no baseline score-by-visit interaction in the model. For the volumetric MRI variables, the model will have a second covariate, a measure of head size (i.e., estimated pseudo total intracranial volume).

The following statistics will be presented on the statistical table of MMRM analysis for change from baseline to each post-baseline visit: descriptive statistics (number of non-missing observations, mean, standard deviation, minimum, and maximum) for each treatment group. LS mean and standard error within group will be presented for each treatment group. LS mean, standard error, 95% confidence interval and two-sided *P* values of treatment difference comparing each ABBV-8E12 dose group with placebo will also be presented for each post-baseline visit. The overall LS mean, standard error, 95% confidence interval and two-sided raw *P* values of treatment difference comparing each ABBV-8E12 dose group with placebo across the treatment period will be included in the output as well.

Responder analysis will be conducted for CGI-C variable. The responses of "Very much improved," "Much improved," "Minimally improved" and "No change" on the CGI-C will be defined as responders. Repeated measure analysis of responders over time on CGI-C responder status will be conducted using a generalized estimation equation (GEE) model with a logit link function to compare the probability of being a responder between each ABBV-8E12 dose and placebo. The model will include fixed, categorical effects for treatment, site, visit and treatment-by-visit interaction in the model using exchangeable working correlation structure. The odds ratio and corresponding 95% confidence interval will be provided for each ABBV-8E12 dose vs placebo at each visit. This responder analysis will not be included in multiplicity adjustment for FWER.

The time to loss of ability to walk independently as measured by PSPRS item 26 will be analyzed using log-rank test to compare median time to loss of ability to walk between placebo and ABBV-8E12 arms.

If both doses are statistically significant on the primary endpoint (PSPRS total score change from baseline at Week 52) after multiplicity adjustment, the contrast between pooled two ABBV-8E12 doses vs. placebo will also be obtained from the MMRM or GEE models for the primary and all secondary efficacy variables.

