10.3.2 Analysis of Exploratory Efficacy Variables

The exploratory efficacy variables include the following:

- Natural History and Neuroprotection in Parkinson Plus Syndromes-Parkinson Plus Scale (NNIPPS-PPS) total score and dimensional scores
- Patient Global Impression of Change (PGI-C) score
- Letter Fluency Test (words per minute) score
- Repeatable Battery for Assessment of Neuropsychological Status (RBANS) total scale score and subtest scores
- Color Trails Test (Parts 1 and 2) completion time
- EuroQuality of Life (EQ-5D-3L) summary index score and VAS score
- Exploratory quantitative MRI measures including diffusion tensor imaging (DTI) derived fractional anisotropy (FA) and diffusivity measures [radial diffusivity (RD), mean diffusivity (MD), and axial diffusivity (AD)]

The MMRM method used for the primary efficacy analysis will be applied to analyze the change from the baseline to each post-baseline assessment up to the last visit of these exploratory variables with the exception of PGI-C for which the dependent variable is the PGI-C score itself. The model will include fixed, categorical effects for treatment, site, visit and treatment-by-visit interaction, with continuous fixed covariate for baseline score and the baseline score-by-visit interaction in the model. There is no baseline score and baseline score-by-visit interaction in the MMRM model for PGI-C analysis. The comparison will be the contrast between each ABBV-8E12 dose group and placebo group at each post-baseline visit.

The following statistics will be presented on the statistical table of MMRM analysis for change from baseline to each post-baseline visit: descriptive statistics (number of non-missing observations, mean, standard deviation, minimum and maximum) for each treatment group. LS mean and standard error within group will be presented for each treatment group. LS mean, standard error, 95% confidence interval and two-sided nominal *P* values of treatment difference comparing each ABBV-8E12 dose group with placebo will also be presented for each post-baseline visit. No multiplicity adjustment will be conducted for multiple comparisons of exploratory efficacy variables.

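### The exploratory PGI-C MMRM adjusts for no baseline severity measure, although baseline CGI-S is collected and already used for CGI-C; if severity predicts PGI-C, avoidable variance stays in

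*Protocol*

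**What the plan says.** **PGI-C.** Protocol 8.1.3.2: "PGI-C scores at each post-baseline visit will be analyzed using an MMRM model, including fixed, categorical effects for treatment, site, visit, and treatment-by-visit interaction". No covariate follows. SAP 10.3.2 states the omission outright: "There is no baseline score and baseline score-by-visit interaction in the MMRM model for PGI-C analysis". The scores are analysed at four visits; SAP 6.2 groups them under "Weeks 12, 24, 36, and 52, i.e., PSPRS, SEADL, PGI-C, PSP-QoL and UPDRS Part II".

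**CGI-C.** Protocol 8.1.3.2 lists the same categorical effects but ends "with continuous fixed covariates for baseline CGI-S". SAP 10.3.1 specifies that "baseline CGI-S score will be used in the MMRM model as a covariate and no baseline score-by-visit interaction in the model". There are eight visits (SAP 6.2: "Weeks 8, 12, 20, 24, 32, 36, 48 and 52, i.e., CGI-S and CGI-C").

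**The plan's usual form.** The primary model in Protocol 8.1.3.1 includes "baseline score-by-visit interaction and treatment-by-visit interaction" as well as the baseline score. SAP 10.3.1 and 10.3.2 apply the same form to the change-from-baseline efficacy variables.

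**Status.** SAP 10.3.1: "UPDRS Part II score, CGI-C score, SEADL score and the midbrain atrophy measured by volumetric MRI are key secondary efficacy variables". PGI-C is exploratory, and SAP 10.3.2 makes no multiplicity adjustment for exploratory variables.

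**Data available.** Protocol Table 7 schedules CGI-S, PSPRS, SEADL and PSP-QoL at screening and again on Day 1 before randomisation.

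**The concern.** A global rating of change has no pre-treatment value, so the usual baseline-score term cannot be used. The plan meets that difficulty for CGI-C by substituting a severity rating. For PGI-C it substitutes nothing, and neither document says why.

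Two things are at stake. The first is precision: a prognostic baseline variable left out of the model stays in the residual. The second is missing data. An MMRM is valid under missing at random given what the model contains. If subjects who are more severe at baseline drop out more often, in a way that their earlier PGI-C scores do not fully capture, the model without baseline severity lacks the information needed. The missing-data sensitivity analyses in SAP 10.5.1 cover PSPRS only, so nothing stands behind the PGI-C model in that respect.

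**Working it through.** **The plan's own figure.** The documents give no power, SD or effect size for PGI-C or CGI-C. The one power figure is about 90% for PSPRS (SAP 4.3: 110 per arm, effect size 0.56 for the high dose, Bonferroni, 25% without Week 52 data). With 110 × 0.75 = 82.5 evaluable per arm and two-sided alpha 0.025, power for the high dose is 91.2%, so the figure reproduces. It is a PSPRS figure and is not affected by this point.

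**PGI-C, complete data.** In a randomised comparison, adjusting for a baseline covariate that correlates at r with the Week 52 outcome multiplies the residual variance by 1 − r². Expressed as evaluable subjects, 82.5 per arm is then worth 82.5 / (1 − r²). Here r is an assumption, shown as a range.

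| r | variance factor 1 − r² | variance avoidable | SE ratio √(1 − r²) | 82.5 per arm is worth |
|---|---|---|---|---|
| 0 | 1.00 | 0% | 1.000 | 82.5 |
| 0.1 | 0.99 | 1% | 0.995 | 83.3 |
| 0.2 | 0.96 | 4% | 0.980 | 85.9 |
| 0.3 | 0.91 | 9% | 0.954 | 90.7 |
| 0.4 | 0.84 | 16% | 0.917 | 98.2 |

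**PGI-C, with dropout.** Simulated trials used three arms of 110, four visits, about 25% monotone dropout driven by the previous score, and within-subject correlation 0.4 or 0.6, with site left out. Adding baseline and baseline-by-visit lowered the variance of the Week 52 contrast by about 3–4% at r = 0.2, 8% at 0.3 and 15–17% at 0.4. The r² rule is therefore a fair guide under dropout too.

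**PGI-C, dropout that depends on baseline severity.** In an illustrative case, dropout depended on baseline severity in the active arms only, and there was no treatment effect. The model without baseline was biased by about 0.01–0.06 SD; adding the covariate removed essentially all of it. This dropout pattern is assumed and does not come from the documents.

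**CGI-C, common slope against visit-specific slopes.** The inputs are eight visits, 25% monotone dropout completely at random, an unstructured covariance, and within-subject correlation either 0.6 throughout or falling to 0.4 between Weeks 8 and 52. The outcome SD is constant or rises from 0.6 to 1. The gain is the reduction in the Week 52 standard error from adding CGI-S-by-visit to the planned model:

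- slope constant over visits: 0%;
- slope doubling from Week 8 to Week 52, r = 0.2–0.3: 0.1–1.3%;
- slope proportional to time, r = 0.2–0.3: 0.4–4.0%, the upper end needing a rising SD as well;
- most extreme case tried (r = 0.5, slope proportional to time, rising SD): 11%.

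**Parameters.** PGI-C with four visits needs one slope per visit: 1 main effect + 3 interaction terms = 4. CGI-C already has one slope, and visit-specific slopes need 8, so 8 − 1 = 7 more.

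**The case against.** The strongest reply is that the omission is deliberate. Protocol 8.1.3.2 excepts both global-change scores from the change-score model, and the two documents agree. A rationale can be supplied, although neither document states one. A change score contains the baseline with a minus sign, so the two are linked by arithmetic; a direct rating of change is not. CGI-S is moreover a clinician's rating, whereas PGI-C is the patient's own, so its correlation with PGI-C may be low. At r = 0.1 the gain is 1% of variance. All of this stands as a reason to keep the claim conditional. It is not a reason to leave the covariate out, since the plan uses CGI-S for CGI-C, which has no arithmetic link either.

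A reader might infer more than the documents support:

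- *That both global-change analyses do lose precision.* No correlation and no visit-specific slopes are given, so the loss is possible but not shown.
- *That a key secondary endpoint is compromised.* CGI-C already adjusts for baseline CGI-S. Only the interaction is absent, and that usually matters little.
- *That missing-at-random bias has been shown.* Dropout that depends on earlier observed scores is already handled by the MMRM. Bias needs dropout tied to baseline severity beyond those scores. The 25% rate is itself a planning assumption for PSPRS.
- *That PGI-C is the only patient-rated global outcome.* The PSP-QoL and EQ-5D visual analogue scales are also analysed. PGI-C is the patient-rated impression of change.
- *That every other MMRM has a baseline-by-visit term.* The model for pre-infusion drug concentration (SAP 12.3) has none. The convention belongs to the change-score efficacy models.

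**Conclusion.** The point holds as a low-cost improvement to an exploratory analysis; it is not an error in the plan. The PGI-C MMRM carries no baseline severity term although a suitable one is collected and used in the neighbouring model. The avoidable share of the Week 52 variance is about r²: nothing at r = 0, 4–9% at r = 0.2–0.3, and 16% at r = 0.4, with r unknown from the documents. With complete data the treatment comparison is unbiased and its type I error is not inflated. Protection against severity-related dropout is a further conditional benefit.

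No confirmatory conclusion depends on PGI-C. For CGI-C the further gain from the interaction is usually 0–2% of the Week 52 standard error, and zero if the slope is constant, so it is only a minor note.

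**What to change.** In Protocol 8.1.3.2 and SAP 10.3.2, add one prespecified covariate, baseline CGI-S, and its interaction with visit to the PGI-C MMRM, and delete the SAP sentence that excludes baseline terms. CGI-S is preferable to choosing among several severity scales because it matches the CGI-C model. The cost is four parameters in a trial of about 330 subjects and no new data; it must be settled before unblinding.

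Optionally, in Protocol 8.1.3.2 and SAP 10.3.1, add baseline CGI-S-by-visit to the CGI-C MMRM so that it matches the change-score efficacy models, at a cost of seven parameters. If the sponsor prefers the present models, one sentence giving the reason would be enough.

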8.1.4 Subgroup Analysis of PSPRS Total Score

To examine whether gender, age group, study site, country/region or other baseline variables have an impact on response to treatment, subgroup analyses on PSPRS total score will be conducted on change from baseline to last observations up to Week 52. Subgroup analyses will be performed using an ANCOVA model with the terms of treatment, site, subgroup variable, the treatment-by-subgroup variable interaction, and baseline score as a covariate. The subgroup analysis for country/region will be performed using the same model but with the study site nested within country/region. The hypothesis that consistent response to treatment across strata of a subgroup variable will be tested at the significance level of 0.100 by examining the *P* value of the treatment-by-subgroup interaction term in the ANCOVA model specified above. The statistical comparison of each ABBV-8E12 dose group with placebo within each subgroup stratum will be performed when the statistical significance of the treatment-by-subgroup interaction term is achieved at 0.100 level. The subgroup analysis will be conducted in the ITT data set.

8.1.5 Biomarker Analyses

An ANCOVA model will be used to evaluate CSF concentrations for total tau, free tau, and NFL for each scheduled time of evaluation during treatment. Corresponding analyses on plasma measurements of total tau and NFL will be performed. The observations will be classified by treatment and region, and the initial model will have an effect for the interaction of treatment and region. The baseline value for total tau and free tau (last value before the first dose of study drug) will be the covariate in the case of total tau and free tau, but for the analysis on the ratio the covariate will be the baseline total tau concentration measurement. If the test statistic on the interaction of treatment and region is not significant at level 0.050, the effect for interaction will be removed from the model. Within the framework of the analysis of covariance the means of the three treatments (with adjustment for baseline) will be estimated. The hypothesis of no difference between the main effects of the higher ABBV-8E12 dose and placebo will be tested at significance level 0.05. If this hypothesis is rejected, the hypothesis of no difference between the lower ABBV-8E12 dose and placebo will then be tested at significance level 0.050. If the statistic on the interaction of treatment and region is significant at level 0.050, the tests for the comparison of the ABBV-8E12 dose levels to placebo will also be performed for each region within the framework of the final model.

If the probability distribution for a variable appears to have considerable non-symmetry (e.g., skewness coefficient > 1.00 in magnitude), a transformation will be sought that has an approximately normal distribution. If a transformation is employed, estimates of central values on the original scale (back transformation of SAS least squares means) will be provided. If the logarithmic transformation is used, the comparison of the treatments will be in terms of the ratio of central values.

If data for other variables are reported, descriptive statistics will be provided and appropriate analyses performed. The association between the variables referred to here as biomarkers and measures of clinical efficacy will be explored.

